Overview: We will enroll up to 30 Veterans and assess feasibility, acceptability, and preliminary efficacy of ME-CCT-A via telehealth. Veterans will receive ME-CCT-A via telehealth and undergo two study evaluations (baseline and 8 weeks) while also continuing with their usual medical, psychiatric, psychotherapeutic, and/or substance use treatment. Feasibility will be assessed by examining data on recruitment and retention rates, rate of completion of the intervention, and feasibility of testing procedures and data collection methods. Acceptability will be assessed through feedback surveys after study completion. We will assess the preliminary efficacy of ME-CCT-A on objective cognitive performance, daily functioning, subjective cognitive complaints, and psychiatric and substance use outcomes.

Intervention: Once at least 4 eligible Veterans have completed baseline visits, the 8-week group will begin via telehealth. The virtual group will be held through VA Video Connect or another VA-approved video meeting tool. Group sessions will last for 2 hours and consist of interactive didactic information and discussion and activities that introduce a variety of cognitive strategies and external aids. [name] (Co-PI) and/or another study staff member will run the CCT groups. Intervention materials will be mailed to participants prior to group start date. Attendance of each Veteran at each session will be noted. Individual make-up sessions will be offered to Veterans who miss a session, and attendance at make-ups will be recorded.

ME-CCT-A Treatment Manual: The structure of the intervention is determined by the ME-CCT-A treatment manual, which has been tailored to each cognitive domain commonly affected by SUDs (Huckans et al., 2018). Session materials correspond to compensatory cognitive training for difficulties with learning, memory, processing speed, executive functioning (multitasking abilities), verbal functioning, concentration, and attention.

Additionally, session content in the updated manual is tailored to address other symptoms related to SUDs that might be influencing cognitive functioning and incorporates motivational interviewing methods. Table 1 outlines the structure and content of the ME-CCT-A treatment manual and group sessions.

[figure not shown]

Table 1. ME-CCT-A Session Content

Session	Major Concepts	Examples of Strategies	Session Activities	Home Exercise

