The cognitive domains were selected for assessment because previous research by our group has demonstrated that SUDs can be associated with significant impairments in attention, memory, and executive functions, and because ME-CCT-A includes cognitive strategy training that specifically targets each of those domains (Huckans et al., 2021; Huckans, Fuller, Wheaton, et al., 2015; Huckans, Fuller, Chalker, et al., 2015; Huckans et al., 2010; Storzbach et al., 2017). Measures were selected because of their sound psychometric properties and their ability to be conducted virtually. Each neuropsychological measure has more than one form, minimizing test-retest confounds at our two assessment visits. Assessment measures will be scored according to standardized test procedures. All assessments will be administered by [name] (Co-PI) or another approved study member and supervised by [name]. (Co-PI), who is a licensed, credentialed, and privileged VA neuropsychologist.

Measure	Construct Assessed
Objective Cognitive Functioning and Functional Capacity (Neuropsychological Tests)	
Wide Range Achievement Test 5 (WRAT5)	Reading ability, premorbid IQ estimate (baseline only)
Neuropsychological Assessment Battery (NAB) Attention Module subtest: Digit Span	Auditory attention capacity and working memory
NAB Attention Module subtest: Driving Scenes	Visual attention and working memory
NAB Memory Module subtest: List Learning	Verbal learning and memory
NAB Memory Module subtest: Shape Learning	Visual learning and memory
NAB Memory Module subtest: Medication Instructions	Verbal learning and memory relevant to everyday functioning
NAB Memory Module subtest: Name, Address, and Phone Number	Verbal learning and memory relevant to everyday functioning
NAB Executive Functions Module subtest: Judgment	Everyday problem-solving/executive function
NAB Executive Functions Module subtest: Categories	Mental flexibility and categorization
Delis-Kaplan Executive Function System (D-KEFS) Verbal Fluency	Language
Self-report Measures (Questionnaire Battery)	
Brief Addiction Monitor (BAM)	Substance use factors; Risk/protective factors
Prospective-Retrospective Memory Questionnaire (PRMQ)	Cognitive symptoms
Portland Cognitive Strategies Scale 2.0 (PCSS)	Compensatory cognitive strategy use
PROMIS-57 Profile v2.1	Physical, mental, and social health
PROMIS v2.0 Cognitive Function 8a	Subjective cognitive functioning

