Client Satisfaction Questionnaire (CSQ-8)	Satisfaction with the intervention (follow-up only)
Timeline Followback (TLFB)	Alcohol and cannabis consumption over a given time period
Alcohol Use Disorders Identification Test (AUDIT-C)	Alcohol use

ANALYTIC PLAN.

All data analyses will be conducted by study personnel with expertise in statistics, using Excel, SPSS, or other statistical software approved by the VA.

Phase 2, Aim 2 Feasibility and Acceptability: Descriptive statistics will characterize the feasibility of recruiting and retaining Veterans. Recruitment will be deemed feasible if we successfully screen for eligibility 50% of Veterans referred to the study and enroll 75% of screened Veterans who meet all study inclusion criteria. Retention will be deemed successful if we achieve 75% completion for post-treatment assessments. Chi-square tests of association and t-tests will compare demographic and clinical characteristics of successfully versus unsuccessfully recruited and retained Veterans to identify characteristics of Veterans who may require more intensive recruitment or retention efforts in a future trial. Acceptability will be assessed through surveys on treatment satisfaction (i.e., CSQ-8 with additional study-specific items) following group completion. Treatment will be deemed acceptable if $\geq 70\%$ of Veterans score ≥ 24 on the CSQ-8.

Phase 2, Aim 3 Preliminary Efficacy: Descriptive statistics and exploratory analyses will be used to assess the normality of the data and homogeneity of variance. Although our small sample size will limit our power to detect significant differences between pre- and post-treatment measures, we will

conduct preliminary analyses using t-tests to examine whether pre-post changes are in the expected directions. We will examine effect size (Cohen's d) and significance of our measures.

Study Population

See sponsor/3rd party protocol for requested information in this section. Indicate what heading/subheading in the 3rd party protocol that the information is located:

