The proposed study is conducted at a single site. We propose to enroll up to 30 Veterans in this pilot trial. Because our primary purposes are to examine feasibility and acceptability to Veterans with AUD, achieving adequate statistical power is not a primary concern of this pilot clinical trial. Results from this study with a sample size of up to 30, combined with comparisons to similar studies of CCT with other Veteran groups (e.g., those with mild TBI history), will provide adequate information on expected effect size to allow for estimations of statistical power for a future proposal of a larger pilot trial.

Inclusion criteria include: 1) Male and female Veterans (>18 years) who meet criteria for AUD in early remission (>1 month, <12 months remission) based on the DSM-5 (American Psychiatric Association, 2013); 2) Concern about a mild cognitive decline that has been identified by the Veteran or a knowledgeable informant (e.g., SUD treatment providers), and the Veteran wants treatment for their cognitive concerns; and 3) Access to internet and webcam.

Exclusion criteria include: 1) Intoxication or impaired capacity to understand study risks and benefits; 2) Major Neurocognitive Disorder, dementia, or neurodegenerative disorder (e.g., Alzheimer's Disease); and/or 3) Auditory or visual impairments that would prevent ability to participate in the cognitive rehabilitation group or benefit from compensatory strategies.

Eligibility will be established by electronic medical record review and will be confirmed by the Veteran during the initial phone call.

1. VA-SPECIFIC REQUIREMENT (inclusion of non-Veterans):

N/A. The study does not include non-Veterans.

See sponsor/3rd party protocol for requested information in this section. Indicate what heading/subheading in the 3rd party protocol that the information is located:

Subject Identification/Recruitment

See sponsor/3rd party protocol for requested information in this section. Indicate what heading/subheading in the 3rd party protocol that the information is located:

Recruitment, eligibility screening, consenting, study visits, and CCT groups will be conducted by approved clinical research staff. A Waiver of Authorization and Informed Consent Process for Screening/Recruitment Purposes will be obtained to facilitate subject identification and recruitment.

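### The plan relies on alternate test forms but does not state which form is given at which visit; if the order is fixed, form difficulty is confounded with pre-post change on nine performance tests

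*Combined protocol and SAP*

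**What the plan says.** All participants are treated: "Veterans will receive ME-CCT-A via telehealth" (Research Design and Methods, Overview). They "undergo two study evaluations (baseline and 8 weeks"), and no comparison group is described.

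On repeated testing, the Assessment Protocol says: "Each neuropsychological measure has more than one form, minimizing test-retest confounds at our two assessment visits". It adds that scoring follows standardized procedures and that the measures were chosen partly for good psychometric properties. It does not say which form is given first, whether the order is fixed, randomized or counterbalanced, whether the forms are equated, or whether norms are form-specific.

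For efficacy, the Analytic Plan (Phase 2, Aim 3) will "conduct preliminary analyses using t-tests to examine whether pre-post changes are in the expected directions", and continues: "We will examine effect size (Cohen's d) and significance of our measures". No form or order term appears. Study Population explains that "achieving adequate statistical power is not a primary concern of this pilot clinical trial", but also says that the results, taken together with similar studies of the training in other Veteran groups, will supply the effect size for planning a larger trial.

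**The concern.** A second form reduces recall of specific items, but it brings in another source of variation: the two forms may not be equally hard. In a two-arm trial that difference would fall on both arms and cancel from the comparison. Here there is one arm and two visits. If everyone takes form A at baseline and form B at follow-up, form and visit are the same variable, and the t-test on change cannot separate them. Only outside information, such as form-specific norms or equated scores, could do so.

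The exposed measures are the eight NAB subtests and D-KEFS Verbal Fluency. WRAT5 is given at baseline only. At stake are the direction, significance and Cohen's d of change on these nine tests, and whatever part of the next trial's sample size rests on them. The direction of any bias is unknown: an easier second form would look like benefit, and a harder one would hide benefit.

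**Working it through.** The plan gives no power, alpha, effect size, test-retest correlation or form-difference figure, so there is nothing to reproduce. The following shows only how large the problem could be under stated assumptions.

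**Inputs from the plan**
- Sample size: "We propose to enroll up to 30 Veterans in this pilot trial" (Study Population).
- Completers: "Retention will be deemed successful if we achieve 75% completion for post-treatment assessments" (Analytic Plan). 0.75 × 30 = 22.5, taken as 23.
- Analysis: paired t-test on pre-post change.

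**Assumed inputs**
- Two-sided alpha of 0.05.
- Zero true change.
- Test-retest correlation r = 0.7, varied from 0.5 to 0.8.
- Form difference δ of 0 to 0.3 SD of a single score, same form order for everyone, no form adjustment in scoring.

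**Step 1: spurious standardized change.** The SD of change, in units of the single-score SD, is √(2(1 − r)). At r = 0.7 this is √0.6 = 0.775. The form difference passes in full into mean change, so d_z = δ / 0.775, which is 0.13, 0.26 and 0.39 for δ = 0.1, 0.2 and 0.3. If Cohen's d is instead scaled by the single-score SD, the spurious d is δ itself. The plan does not say which version it will use.

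**Step 2: rejection rate.** The t statistic follows a non-central t distribution with n − 1 degrees of freedom and non-centrality d_z√n. For δ = 0.2 and r = 0.7 the non-centrality is 0.258 × √23 = 1.24 at n = 23 and 0.258 × √30 = 1.41 at n = 30.

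Probability of a significant result in either direction when nothing has changed:

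| r | n | δ = 0 | 0.1 | 0.2 | 0.3 |
|---|---|---|---|---|---|
| 0.5 | 23 | 5.0% | 7.4% | 15.1% | 28.0% |
| 0.5 | 30 | 5.0% | 8.3% | 18.5% | 35.5% |
| 0.7 | 23 | 5.0% | 9.1% | 22.0% | 42.7% |
| 0.7 | 30 | 5.0% | 10.5% | 27.7% | 53.6% |
| 0.8 | 23 | 5.0% | 11.2% | 30.6% | 58.5% |
| 0.8 | 30 | 5.0% | 13.3% | 38.8% | 70.9% |

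The rates are the same if the sign of δ is reversed. A real gain of 0.2 SD would then be cancelled exactly by a second form that is 0.2 SD harder.

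**Step 3: effect of balancing.** With half the sample in each order, the individual shifts are +δ and −δ and the mean shift is zero. A simulation of 200,000 runs (r = 0.7, n = 30, no form term) gave no bias, with rejection rates of 4.8%, 4.3% and 3.6% for δ = 0.1, 0.2 and 0.3. The bias has gone, but the test is conservative because the form effect now inflates the variance of change.

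**Step 4: why an order term is also needed.** If dropout leaves 13 completers in one order and 10 in the other, (13 − 10) / 23 = 13% of the form difference stays in the raw mean change. Fit change = μ + γz, with z = +1 for one order and −1 for the other. The estimate of μ is then the plain average of the two order means, and the form effect cancels whatever the split. The price in precision is small: the variance factor is ¼(1/13 + 1/10) = 0.0442, against 1/23 = 0.0435 for the raw mean.

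**The case against.** The plan is silent on order; it does not set a fixed one. A reader might infer that the forms are not counterbalanced and that form difficulty will therefore be read as a treatment effect. The documents do not support that. The team may already alternate forms, and the figure of study procedures cited under Step-by-Step Guidance, along with part of Preliminary Studies, was not available to check.

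Nor does the plan claim that alternate forms remove retest confounding, only that they minimize it. That claim can be true in either order, because a new form reduces item recall regardless. Form difficulty is a separate threat.

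Scoring under standardized procedures might include form-specific norms, which would reduce or remove the problem; the documents neither say so nor exclude it. Nothing in them shows that the forms differ at all, and with no difference the error rate is the nominal 5%.

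Finally, the main purposes are feasibility and acceptability, the efficacy tests are labelled preliminary, and the effect sizes are to be read alongside other studies.

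All of this stands, and it limits the point to a conditional one about a secondary aim. It does not answer the gap: the stated safeguard is incomplete without an order rule, and a fixed order cannot be undone once testing is finished.

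**Conclusion.** The point holds conditionally. The visible plan does not assign form order and has no form term. If the order is common to all and scores are not adjusted for form, form difficulty is fully confounded with pre-post change on nine performance tests. For an assumed 0.2 SD form difference, the chance of a false significant change is 15% to 39% over r = 0.5 to 0.8 and n = 23 to 30, against 5% with no difference. The correlation, the form differences, alpha and sidedness are all assumptions, and the sign of any bias is unknown.

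It would go too far to conclude that the efficacy results will be biased, or that the next trial will be mis-sized. The first needs an order and a scoring rule that the plan does not state, and the second ignores the other studies that will inform the effect size. The feasibility, acceptability and self-report outcomes are untouched. This is a worthwhile improvement to a preliminary aim, not a threat to the trial's main purpose.

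**What to change.** Add to the Assessment Protocol that form order is assigned 1:1 before baseline testing, from a short random list balanced within each therapy cohort. Since a group starts once at least four Veterans have completed baseline, small blocks restarted for each new cohort would do this. Record the form given at each visit for every test. If the team already counterbalances, it need only say so. If baseline testing has begun, record the forms used so far and balance the remainder.

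In the Analytic Plan, replace the plain pre-post t-test on these nine measures with the same test of mean change from a model containing a +1/-1 form-order term. Report the order coefficient too, since it estimates the form difference for the next trial. State whether scoring uses form-specific norms, and which version of Cohen's d is reported.

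The cost is a few sentences, database fields for the form given, and one degree of freedom, with no extra visits or participants. It does not deal with residual practice effects, natural recovery in early remission or concurrent usual care. Those remain uncontrolled without a comparison group, and the report should say so.

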Motivationally Enhanced Compensatory Cognitive Training for Addictions (ME-CCT-A) is a manualized group-based behavioral intervention (8 weeks, 2 hour per week) designed to improve cognitive functioning in Veterans with substance use disorders (SUDs) and cognitive complaints. ME-CCT-A is an adaptation of CCT initially developed by clinicians and researchers at the VA Portland Healthcare System and VA San Diego Healthcare System (Storzbach et al., 2017). CCT draws from the empirical and theoretical literature on compensatory strategy training for conditions characterized by cognitive complaints and impairments, including mild traumatic brain injury (Storzbach et al., 2017), psychosis

(Twamley et al., 2012), and mild cognitive impairment (Huckans et al., 2010). ME-CCT-A is a comprehensive treatment in that it addresses multiple types of symptoms and concerns that interfere with recovery from addictions – cognitive impairments, neuropsychiatric symptoms, and lifestyle patterns that increase risk of cognitive impairment, poor health, and relapse. In addition to training in compensatory cognitive skills, ME-CCT-A includes mindfulness practices and motivational interviewing techniques (Miller, 2013) to boost the adoption of lifestyle strategies (e.g., nutrition, exercise) that improve cognition and overall health (Gomez-Pinilla, 2006). ME-CCT-A is designed to be easy to administer and as an adjunct to standard SUD treatment programs. While initially designed to be delivered in-person, ME-CCT-A can be delivered through virtual platforms with little to no modification of the content and structure of the intervention.

VA-SPECIFIC REQUIREMENT (relevance to VA mission):

See sponsor/3rd party protocol for requested information in this section. Indicate what heading/subheading in the 3rd party protocol that the information is located: [REDACTED]

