1	Intro and SUD/cognitive functioning psychoeducation	Creating a "home" for important items	Day planner use	Finding a home for the day planner
2	Organization and prospective memory Part I	Time management	Scheduling and concrete goal setting	Practice using the calendar
3	Organization and prospective memory Part II	Daily and weekly planning sessions	Enter lists and activities into the calendar	Follow through with planning sessions
4	Attention and concentration	Paying attention during meetings and conversations	Practicing paying attention during conversations	Active listening once a day
5	Learning and memory	Internal and external memory strategies	Practice memory strategies	Practice using a strategy everyday
6	Problem-solving and cognitive flexibility	Evaluating costs and benefits to identify better choices	6-step problem-solving method	Practice problem-solving with 2 life goals
7	Planning and goal setting	Goal setting	Identify and re-evaluate priorities	Practice planning a goal
8	Skill integration and review	Review, practice, goals, and planning for the future	How to maintain skills and apply them to goals	Provided with additional SUD-related resources

Assessment Protocol: Veterans will complete the virtual assessment battery (see Table 2) at baseline (approximately 0-2 weeks prior to ME-CCT-A) and follow-up (approximately 0-2 weeks following ME-CCT-A completion). The battery consists of performance-based tests of objective cognition functioning and functional capacity and self-report measures of subjective cognitive complaints/functioning, substance use, engagement in targeted lifestyle practices associated with improved cognition, and engagement in protective activities/factors associated with reduced relapse. The Client Satisfaction Questionnaire (CSQ-8) and a series of structured, open-ended questions specific to the study intervention will be included at follow-up to assess Veterans' satisfaction with the virtual CCT intervention. Assessments will take approximately 2 hours.

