4. The Corporate Data Warehouse (CDW) will be utilized to compile a list of potential participants. IRB-approved study staff will use this list to conduct medical chart reviews (i.e., CPRS) to identify Veterans who meet study criteria, do not meet exclusion criteria, are able to provide informed consent, can attend visits virtually, and may be interested in participating in the research. Veterans who are identified as eligible will be sent a letter from the Mental Health Clinical Director, a letter of introduction from the study team, the study flyer, and a form with the option to opt-in or opt-out to hearing more about the research either by calling study staff or returning the enclosed opt-in/opt-out form. A self-addressed, postage-paid return envelope will be included for the Veteran's convenience. The letter will also state that if study staff does not receive a response within two weeks, the Veteran may be contacted by phone to verify receipt of the letter and be given the option to be mailed a second letter (if not received). Only verification of Veteran's address will be obtained for those who did not receive a letter. Study staff will call all Veterans who indicate interest to provide more information about the study, answer any questions the Veteran may have, and, if applicable, schedule the initial baseline visit.

An appointment confirmation letter will be mailed to a participant after they have scheduled their initial visit. An appointment confirmation letter will also be sent prior to their follow-up visit. If a participant is enrolled in the study and not returning phone calls to schedule additional research visits, a no-show letter will be sent in the mail asking the participant to contact the research coordinator to discuss their interest in their continued involvement in the research study. If the research coordinator does not hear back from the participant within two weeks of sending the letter, the participant will be disenrolled from the research study.

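### Does the 75% retention rule need a stated denominator, given that Veterans who cannot be reached are disenrolled?

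*Combined protocol and SAP*

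**What the plan says.** The feasibility paragraph of the Analytic Plan gives the retention rule in one sentence: "Retention will be deemed successful if we achieve 75% completion for post-treatment assessments". The sentence before it, on recruitment, does name its bases: Veterans referred, and screened Veterans who meet the inclusion criteria. The sentence after it plans chi-square and t-tests of "successfully versus unsuccessfully recruited and retained Veterans".

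Subject Identification/Recruitment contains a contact procedure: "If a participant is enrolled in the study and not returning phone calls to schedule additional research visits, a no-show letter will be sent". After two weeks without a reply, "the participant will be disenrolled from the research study".

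On timing, the Overview in Research Design and Methods has Veterans "undergo two study evaluations (baseline and 8 weeks"), and the Assessment Protocol places "follow-up (approximately 0-2 weeks following ME-CCT-A completion").

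On completion, the Overview states: "Feasibility will be assessed by examining data on recruitment and retention rates, rate of completion of the intervention, and feasibility of testing procedures". The treatment is described in the rationale as a "manualized group-based behavioral intervention (8 weeks, 2 hour per week"). The Intervention paragraph has attendance noted for each Veteran at each session, and individual make-up sessions offered and recorded. The Analytic Plan gives no definition of completion and no target for it.

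**The concern.** Feasibility and acceptability are the stated primary purposes, and retention is one of the few outcomes with a pass mark. A percentage rule without a denominator invites the question of who is in it.

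The disenrollment procedure sharpens that question. There are only two evaluations, so for a Veteran past baseline the remaining visit is the follow-up that retention counts. A Veteran who cannot be reached to schedule it is therefore both a retention failure and a candidate for disenrollment. If the rate were taken over those still enrolled, the rule would discard the failures it is meant to measure, and that choice could be made after the data were seen. A poorly retained pilot could then be reported as feasible to those planning the larger trial.

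Two lesser worries go with this. Follow-up is dated at 8 weeks in one place and from completion of the intervention in another, which might suggest a third base of completers only. And the rate of intervention completion is listed as a feasibility measure without a session count or a rule on make-ups.

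**Working it through.** The plan derives no sample size, power or error rate for the retention rule, so there is no figure to reproduce.

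**Inputs from the plan.** Pass mark 75% (Analytic Plan); enrollment of up to 30 (Study Population). **Assumptions.** All 30 places are filled; the number disenrolled, *d*, the true follow-up rate, *p*, and the share of those not followed up who are disenrolled, *f*, are not in the documents and are varied.

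**1. Assessments needed to pass.** The minimum is 0.75 × (30 − *d*), rounded up, if disenrolled Veterans are left out. With *d* = 0 this is the all-enrolled rule.

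| Disenrolled and excluded | Denominator | Needed | As a share of 30 |
|---|---|---|---|
| 0 | 30 | 23 | 76.7% |
| 1 | 29 | 22 | 73.3% |
| 2 | 28 | 21 | 70.0% |
| 6 | 24 | 18 | 60.0% |
| 10 | 20 | 15 | 50.0% |

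The smallest reversal needs one disenrollment: 22/30 = 73.3% fails, 22/29 = 75.9% passes.

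**2. Chance of passing.** On all enrolled this is P(X ≥ 23) with X ~ Bin(30, *p*). With exclusion, D ~ Bin(30, (1 − *p*)*f*), the number assessed given D is Bin(30 − D, *p*/(1 − (1 − *p*)*f*)), and the rule passes when that number is at least 0.75 × (30 − D).

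| *p* | All enrolled | *f* = 25% | *f* = 50% | *f* = 75% |
|---|---|---|---|---|
| 50% | 0.3% | – | 22% | – |
| 60% | 4% | 20% | 54% | 92% |
| 70% | 28% | – | 85% | – |

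So the choice of base would matter a good deal if it were open. The remaining steps ask whether it is.

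**3. Which base the text supports.** The rules in the feasibility paragraph form a sequence: referred, screened, enrolled, then assessed after treatment. Each rate is taken over the group before it, so the base for the last is those enrolled. The next sentence compares retained with non-retained Veterans. That comparison needs the non-retained to be kept and identified, which a still-enrolled base would partly undo. The disenrollment text sits among contact and scheduling procedures and defines no analysis set. Nothing there or in the Analytic Plan removes anyone from a rate.

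**4. Whether a completers-only base is a real reading.** The same Assessment Protocol sentence that dates follow-up from completion dates baseline from the start of the intervention, which is a point on the group's calendar. The Intervention paragraph describes one 8-week group, and the Analytic Plan times the satisfaction survey, itself a follow-up measure, after the group ends. Read together, follow-up falls in roughly the two weeks after the 8-week group finishes, for every Veteran in it. The two statements of timing agree.

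**5. Completion of the intervention.** There is no pass mark, so no definition can reverse a verdict. Because attendance is held by Veteran and session, with make-ups recorded, the rate can be computed for any session count, with or without make-ups.

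**The case for a change.** The strongest case for a change is that the sponsor named the denominators for recruitment in the preceding sentence and did not do so for retention. Planning a descriptive comparison of those lost does not in strict terms fix the base of a pass/fail rule. If all enrolled is meant, one sentence would say so and remove any freedom to choose later, on an outcome that serves the trial's primary purpose.

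The factual part stands: the denominator is not written down, and the plan does not expressly rule out excluding disenrolled Veterans. What does not follow is that the plan leads to a wrong result. The reversal needs an analyst to adopt a base that the text never mentions and that sits badly with the comparison in the next sentence. The large contrasts, such as 4% against 54% or 92%, also need an assumed 60% true follow-up and assumed shares of lost Veterans being both disenrolled and excluded. The documents give no basis for those values.

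It can also be said that consented, baseline-completed and group-started Veterans may differ, since a group waits for at least four baselines. That is true, but it is an ordinary reporting matter, settled by giving the counts at each step.

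**Conclusion.** The concern does not call for a change. The retention sentence leaves out its denominator, but its place in the sequence and the planned comparison of retained and non-retained Veterans point to all enrolled, with disenrolled Veterans counted as not retained. On that reading the rule gives one verdict for any data set: with 30 enrolled, 23 assessed (76.7%) passes and 22 (73.3%) fails. The excluded-base results are arithmetically right but depend on a reading that the plan does not make and on inputs that it does not give.

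The stakes are limited as well. The plan attaches no stop-or-go action to the 75% mark, and reporting the numbers enrolled, disenrolled and assessed would let any reader recompute the rate. The undefined completion rate is descriptive and can be recovered from the recorded attendance. The two statements of follow-up timing are consistent once the end of the group is taken as the anchor.

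This rests on the visible text. The study timeline figure is not shown and the treatment manual is not part of the documents, so neither was checked.
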